8.3 Handling of Missing and Incomplete Data

Subjects may miss specific data points for a variety of causes. In general, data could be missing due to a subject's early withdrawal from study, a missed visit, or inability to evaluate an endpoint at a particular point in time. For this study, most of the efficacy endpoint will be collected via eDiary and subjects could miss entering several days of data in each monthly interval. The general procedures outlined below describe what will be done when a data point is missing.

In general, the PAS will be used without any subject-level imputation for missing data for the primary and secondary endpoints, except for proration performed for the eDiary measurements, as described below. The sensitivity analyses for both primary and secondary analyses will use non-responder imputation for categorical endpoints and multiple imputation with the assumption of missing not at random (MNAR) (with control- based pattern imputation) for the continuous endpoints.

Missing eDiary data in the calculation of monthly measurements about subjects' migraine and non-migraine headaches and missing daily scores of impairment day based on MPFID will be handled based on the degree of completion during the month.

For the eDiary, if at least 14 out of 28 monthly days are not missing, then the monthly frequency measurements (eg, migraine days, headache days, migraine attacks) will be prorated based on the number of days with available information using the following formula:

Number of observed migraine days *28/Number of information days in interval,
where an information day is a diary day or headache day.

For each MPFID daily diary domain, if greater than 50% of the items within a domain are not missing, the mean of the item scores that are present for that day will be used to impute a score for the missing item(s). Otherwise, no domain score will be calculated; the domain score will be considered missing.

Table 8-1. Handling of Missing and Incomplete eDiary Data

Monthly Endpoint	Condition	Proration Method (does not need to be rounded)

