Monthly frequency measurements (including migraine days, headache days, migraine attacks, acute headache medication treatment days, acute migraine-specific medication treatment days)	If diary days in entire baseline or interval post baseline ≥ 14 (including retrospective eDiary days), then do proration; Else monthly measurement is set to missing [A diary day is a day with all headache related questions completed retrospectively or not]	Number of observed migraine days * 28/ Number of information days in interval [information day is a diary day or headache day]
Monthly average of severity of migraine pain (1-3 scale)	If diary days in entire baseline or interval post baseline ≥ 14 (including retrospective eDiary days), then calculate the average; Else missing	Arithmetic mean of the observed pain scores of qualified migraine headaches over the monthly interval
Monthly average of MPFID domain scores	If days with observed daily domain score in interval ≥ 14 then calculate the average; Else missing	Arithmetic mean of the observed daily domain score over the monthly interval
Monthly impairment day for Everyday Activity and Physical Impairment domains and overall	If days with observed daily domain score in interval ≥ 14 then do the proration; Else missing	Number of observed impairment days * 28/ Number of days with domain score in monthly interval

Completely missing COAs and subject-completed assessments (eg, HIT-6, MIDAS) scheduled to be collected at office visit at certain assessment will not be imputed.

Missing safety endpoints and antibody data will not be imputed, except for adverse event dates as described in [Section 8.3](#).

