9.5 Efficacy Analyses

Endpoint	Statistical Analysis Methods
Primary	
The primary endpoint, change in monthly migraine days from the baseline period to the last 4 weeks of the 12-week DBTP, will be analyzed using the generalized linear mixed effects model including treatment group, baseline value, stratification factors, scheduled visit, and the interaction of treatment group with scheduled visit using the PAS without any subject-level imputation for missing data. The primary endpoint will be tested for each AMG 301 treatment group (AMG 301 420 mg SC injections Q2W and AMG 301 210 mg SC injections Q4W) compared to the placebo group using appropriate contrasts for pairwise comparisons. Each AMG 301 dose will be compared to placebo at an alpha of 0.05 to maintain the family-wise type I error at 0.10. The mean change from the baseline period for each treatment group, and the treatment difference, 95% confidence intervals, and p-values will be reported.
 
Sensitivity analyses for the primary endpoint include an analysis of covariance model using data through week 12, in which missing values will be imputed using multiple imputation assuming MNAR up to week 12.

Secondary	
• At least a 50% reduction from the baseline period in monthly migraine days in the last 4 weeks of the 12-week double-blind treatment period: Comparison between treatment groups will be performed using CMH tests on observed data with stratification factors. The odds ratio for each AMG 301 treatment group versus placebo group, associated 95% confidence intervals, and unadjusted p-values will be reported. Sensitivity analyses for response include: a logistic regression model using data from week 9 through week 12, adjusting for baseline values where missing values will be imputed as non-responders.
• Change from the baseline period in monthly acute migraine-specific medication days in the last 4 weeks of the 12-week double-blind treatment period: The same analysis methods will be used as for the primary endpoint. Refer to Table 5 for details on other secondary endpoints.
CCI	

The primary analysis of efficacy endpoints will utilize the PAS. Subjects will be analyzed according to their randomized treatment group regardless of the actual treatment received during the study.

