For primary analysis at week 12, the continuous change from baseline efficacy endpoints calculated by the method as specified in [Section 5.6](#) will be analyzed using generalized linear mixed effect models including treatment group, stratification factors, scheduled visit, the interaction between treatment group and scheduled visit and the baseline value on observed data. The dichotomous efficacy endpoints will be analyzed using the stratified Cochran-Mantel-Haenszel (CMH) test after the missing data are imputed as non-response. Detailed primary analysis methods, sensitivity analyses, and covariates included in the models are summarized in the table below.

Table 9-1. Summary of Efficacy Endpoints and Analysis Methods

Endpoint	Primary Summary and Analysis Method	Sensitivity Analysis
Primary Endpoint		
Change in monthly migraine days from baseline to the last 4 weeks of the 12-week DBTP (Note: Results from time points other than week 12 during the DBTP will also be generated in the same generalized linear mixed effect model.)	Analysis Method I: 1. Summary statistics by visit using observed data 2. Least squares means from a generalized linear mixed effect model including treatment group, baseline values, stratification variables, scheduled visit, and interaction of treatment and scheduled visit using observed data	1. Summary statistics by visit and analyze using an ANCOVA model with multiple imputation assuming MNAR(control-based pattern imputation) 2. Summary statistics by visit and analyze using an ANCOVA model with observed data 3. Subgroup analyses: Same as primary summary and analysis method.

Page 1 of 3

Footnotes defined on last page of the table

Table 9-1. Summary of Efficacy Endpoints and Analysis Methods

Endpoint	Primary Summary and Analysis Method	Sensitivity Analysis
Secondary Endpoints		

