At least a 50% reduction from baseline in monthly migraine days in the last 4 weeks of the 12-week DBTP (Note: Results from time points during DBTP will also be generated in the same model.)	1. Summary statistics by visit using observed data 2. Stratified Cochran-Mantel-Haenszel (CMH) Test	1. Summary statistics by visit and analyze using a logistic regression model, and using responder rate calculated using monthly migraine days 2. A stratified Cochran-Mantel-Haenszel (CMH) test will be used after the missing data are imputed as non-response 3. A generalized linear mixed effects model will be used on observed data 4. Subgroup analyses: Same as primary summary and analysis method.
Change from baseline in monthly acute migraine-specific medication treatment days in the last 4 weeks of the DBTP (Note: Results from individual time point during the DBTP will also be generated in the same generalized linear mixed effect model.)	Analysis Method I (see above)	Analysis Method II: 1. Summary statistics by visit and analyze using an ANCOVA model with multiple imputation, assuming MNAR
Change from baseline in monthly physical impairment scores as measured by MPFID at assessment time points (Note: Results from individual time point during the DBTP will also be generated in the same generalized linear mixed effect model.)	Analysis Method I	N/A

Footnotes defined on last page of the table

Page 2 of 3

Table 9-1. Summary of Efficacy Endpoints and Analysis Methods

Endpoint	Primary Summary and Analysis Method	Sensitivity Analysis
Change from baseline in monthly impact on everyday activities scores as measured by MPFID at assessment time points (Note: Results from individual time point during the DBTP will also be generated in the same generalized linear mixed effect model.)	Analysis Method I	N/A
CCI	Analysis Method I	N/A
	
• Summary statistics by visit using observed data• Stratified CMH test	N/A

Page 3 of 3

^a The same analyses methods will be applied to the endpoints:

Change from baseline in headache impact scores as measured by HIT-6
Change from baseline in monthly average severity of migraine pain
Change from baseline in monthly acute headache medication treatment days.
Change from baseline in migraine-related disability and productivity as measured by MMIDAS
Change from baseline in monthly days with physical impairment as measured by the MPFID

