9.5.2 Analyses of Secondary Efficacy Endpoint(s)

For continuous secondary efficacy endpoints, summary statistics and primary analysis method will be conducted in the same way as that for the primary endpoints as specified in [Section 9.5.1](#).

For dichotomous secondary endpoints, comparison between treatment arms will be performed using a stratified CMH test for the primary analysis. Sensitivity analyses will use generalized linear mixed effects model on observed data, adjusting for baseline values and stratification factors with appropriate contrasts for pairwise comparisons. The odds ratio for each AMG 301 treatment group versus placebo group, associated 95% confidence intervals, and unadjusted p-values will be reported. Sensitivity analyses for response include: a logistic regression model using data through week 12, adjusting for baseline values where missing values will be imputed as non-responders.

Subgroup analyses are performed for secondary efficacy endpoints using the same method as primary analysis method but performed within each interested subgroup. The treatment difference (or odds ratio) with associated 95% confidence interval and p-values will be reported within each subgroup.

CCI

A large black rectangular box redacting content. The text 'CCI' is visible in the top-left corner of the redacted area.

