9.5.4 Analyses of Clinical Outcome Assessments (COAs) and Patient Reported Outcomes (PROs)

The COAs and PROs include MPFID, HIT-6, MMIDAS and CAPS. Change from baseline in total score (or subscale if applicable) of each COA and PRO (except endpoints described in the [Section 9.5.1](#) above) will be reported during the DBTP.

For HIT-6, in addition to the analysis of continuous change from baseline value, proportions of subject with a \geq 5-point reduction from baseline and proportions of subject with HIT-6 \geq 60 (severe impact) will be analyzed similarly as the primary analysis method for dichotomous efficacy endpoints described in [Section 9.5.2](#) above. No sensitivity analysis will be conducted for COA and PROs except for MPFID. The PAS will be used to analyze COA and PRO endpoints.

Table 9-2. Summary of COA and PRO Endpoints and Analysis Methods

Endpoint	Primary Summary and Analysis Method
Change from baseline in the daily activity impact of a headache as measured by the HIT-6 total score	1. Summary statistics by visit using observed data 2. Least squares mean at each time point calculated based on a linear mixed effects model including treatment group, baseline value, stratification factors, scheduled visit, and the interaction of treatment group with scheduled visit, without any subject-level imputation for missing data.
Change from baseline in CAPS	Same as above
Change from baseline in migraine-related disability and productivity as measured by the modified MIDAS (Note: MIDAS scores are collected every month. The first post-baseline measurement of the modified MIDAS scores are at week 4)	Same as above; using ANCOVA model instead of generalized linear mixed effect model.
Change from baseline in monthly mean overall impact on everyday activities score as measured by MPFID stand-alone item	Same as above; using ANCOVA model instead of generalized linear mixed effects model.
Change from baseline in monthly days with physical impairment as measured by MPFID	Same as above; using ANCOVA model instead of generalized linear mixed effects model.
HIT-6 severity grade shift from baseline	Summary statistics for DBTP only. Shift table will also be provided to compare baseline values vs the most extreme post-baseline values through the DBTP.
MMIDAS severity grade shift from baseline	Summary statistics for DBTP only. Shift table will also be provided to compare baseline values vs the most extreme post-baseline values through the DBTP.

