9.7.2 Analyses of Clinical Outcome Assessments

See Section 9.5.4.

10. Changes From Protocol-specified Analyses

The endpoint of change from the baseline period in monthly days with impact on everyday activities as measured by the MPFID domain at assessment time points was not included in the protocol but was added to the SAP to assess the effect of AMG 301 compared to placebo on change from the baseline period in monthly days with impact on everyday activities as measured by the MPFID domain.

The protocol stated that for secondary endpoints comparison between treatment groups for categorical data will be performed using generalized linear mixed effects model on observed data adjusting for baseline values and stratification factors with appropriate contrasts for pairwise comparisons as well as CMH test. The analysis method will be changed so that comparison between treatment groups for secondary endpoints will be performed using only CMH tests on observed data with stratification factors for categorical data.

The protocol stated that the FAS consists of all subjects who were enrolled in the study. This definition will be changed so that the FAS consists of all subjects who were randomized in the study.

Three subgroups were added: prior use of anti-CGRP medication, CAPS score at baseline, and response status to AMG 334.

11. Literature Citations / References

AMG 301 Investigator Brochure. Thousand Oaks, CA. Amgen Inc.

Amgen. A Phase 2, Randomized, Double-blind, Placebo-controlled Study to Evaluate the Efficacy and Safety of AMG 334 in Chronic Migraine Prevention. AMG 334 Study 20120295. 23 July 2015.

Amgen. A Phase 3, Randomized, Double-blind, Placebo-controlled Study to Evaluate the Efficacy and Safety of AMG 334 in Migraine Prevention. AMG 334 Study 20120296. 24 March 2015.

Edvinsson L. Role of VIP/PACAP in primary headaches. *Cephalgia* 2013;33:1070-1072.

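### SAP 9.5 gives two missing-data rules for the primary responder analysis, and the planned odds ratio is not the difference in proportions named in SAP 2.1

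*SAP*

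**What the plan says.** **Missing-data rule.** The paragraph of SAP 9.5 that opens with the week-12 primary analysis uses observed data for continuous endpoints and then says: "The dichotomous efficacy endpoints will be analyzed using the stratified Cochran-Mantel-Haenszel (CMH) test after the missing data are imputed as non-response". Other parts of the SAP differ:

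- SAP 8.3: "the PAS will be used without any subject-level imputation for missing data for the primary and secondary endpoints", apart from diary proration. The same section assigns non-responder imputation to the sensitivity analyses of categorical endpoints.
- SAP 9.5 methods table, secondary row for the 50% responder endpoint: "Comparison between treatment groups will be performed using CMH tests on observed data with stratification factors".
- SAP Section 10, the declared changes from the protocol: the comparison "will be performed using only CMH tests on observed data with stratification factors for categorical data".
- Table 9-1, sensitivity column, item 2 for the same endpoint: "A stratified Cochran-Mantel-Haenszel (CMH) test will be used after the missing data are imputed as non-response".

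Two places name the test without a missing-data rule: the primary column of Table 9-1, and SAP 9.5.2, where "comparison between treatment arms will be performed using a stratified CMH test for the primary analysis". SAP 9.5.4 says that the HIT-6 proportions "will be analyzed similarly as the primary analysis method for dichotomous efficacy endpoints described in" Section 9.5.2.

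**Effect measure.** SAP 2.1 sets the summary measure for the 50% responder objective as the difference in proportions between each AMG 301 group and placebo. SAP 9.1, 9.5 and 9.5.2 plan odds ratios with 95% confidence intervals and p-values. The descriptive output is counts and percentages per group.

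**The concern.** The 50% responder rate is the first-listed secondary endpoint and is also one of the endpoints in the administrative interim analyses. For it, both CMH analyses are prespecified, so the doubt is which one is labelled primary. If missingness differs by arm the two can give different headline results, and that choice should not be open after unblinding.

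For some dichotomous endpoints there is less cover. SAP 9.5.4 plans no sensitivity analysis for clinical outcome assessments and patient-reported outcomes other than MPFID. Table 9-1 likewise enters none for the dichotomous endpoints in its last row. For these, the rule can decide the only analysis listed there. If the 9.5 sentence applied to HIT-6, missing HIT-6 data would be imputed, whereas SAP 8.3 says that completely missing assessments "scheduled to be collected at office visit at certain assessment will not be imputed".

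The second gap is that the SAP defines one quantity as its estimand and plans interval estimates of another.

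**Working it through.** **1. Text comparison, 50% responder endpoint**

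| SAP location | Primary method | Missing data in the primary analysis |
|---|---|---|
| 8.3 | not named | no subject-level imputation; non-responder imputation is a sensitivity analysis |
| 9.5 methods table | CMH | observed data |
| 9.5 running text | stratified CMH | imputed as non-response |
| Table 9-1 | stratified CMH | none stated; CMH with imputation is sensitivity item 2 |
| 9.5.2 | stratified CMH | none stated |
| 10 | CMH only | observed data |

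The 9.5 running text stands alone and is probably leftover wording.

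**2. How far the two rules can differ**

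The documents show no response or missing-data rates (the sample-size sections are redacted), so there is no plan figure to reproduce. The rates below are assumptions.

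Inputs: 335 subjects at 4:3:3 (SAP 3.1) give 335×4/10 = 134 on placebo and 335×3/10 = 100.5, taken as 100, per active arm. Let p0, p1 be observed response and m0, m1 the missing fractions (0 = placebo, 1 = active).

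- Observed data: rates p0, p1 on 134(1−m0) and 100(1−m1) subjects.
- Non-responder imputation: rates p0(1−m0), p1(1−m1) on 134 and 100 subjects.
- Test: z = (rate1 − rate0)/√[p̄(1−p̄)(1/n0+1/n1)], with p̄ the pooled rate. This is an unstratified approximation to CMH.

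Worked case, 30% vs 43%, missing 6% placebo and 12% active:

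- Observed: n = 126.0 and 88.0; difference 13.0 points; p̄ = 0.3535; SE = 0.0664; z = 1.957; p = 0.050. OR = (0.43/0.57)/(0.30/0.70) = 1.76.
- Imputed: 0.30×0.94 = 28.2% and 0.43×0.88 = 37.8%; difference 9.6 points; p̄ = 0.3232; SE = 0.0618; z = 1.560; p = 0.12. OR = 1.55.

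| Observed response (placebo vs active) | Missing (placebo/active) | Observed data | Non-responder imputation |
|---|---|---|---|
| 30% vs 43% | 6%/6% | 13.0 points, p=0.046 | 12.2 points, p=0.050 |
| 30% vs 43% | 6%/12% | 13.0, p=0.050 | 9.6, p=0.12 |
| 30% vs 43% | 12%/6% | 13.0, p=0.050 | 14.0 (OR 1.89), p=0.023 |
| 30% vs 43% | 5%/15% | 13.0, p=0.052 | 8.1, p=0.19 |
| 30% vs 43% | 15%/5% | 13.0, p=0.051 | 15.4, p=0.013 |
| 30% vs 40% | 6%/12% | 10.0, p=0.13 | 7.0, p=0.25 |
| 30% vs 40% | 12%/6% | 10.0, p=0.13 | 11.2, p=0.067 |
| 30% vs 45% | 6%/12% | 15.0, p=0.025 | 11.4, p=0.067 |
| 30% vs 45% | 12%/6% | 15.0, p=0.024 | 15.9, p=0.011 |

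With equal missingness the rules nearly agree. With unequal missingness they part in either direction, so neither is safely conservative.

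**3. Odds ratio versus difference**

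For a fixed odds ratio of 1.76, let o = 1.76×p0/(1−p0) and p1 = o/(1+o):

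- p0 = 20%: o = 0.440, p1 = 30.6%, difference 10.6 points.
- p0 = 30%: o = 0.754, p1 = 43.0%, difference 13.0 points.
- p0 = 40%: o = 1.173, p1 = 54.0%, difference 14.0 points.

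The odds ratio and its interval therefore do not give the stated estimand without the placebo rate.

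**The case against.** **The intent can be inferred.** The sentence after the conflicting one refers the detail to Table 9-1, which places CMH with imputation in the sensitivity column, and Section 10 and the endpoint-specific row agree. This makes the likely intent clear. However, the primary cell to which the reader is sent carries no missing-data rule for the test, and the SAP has no precedence clause, so the contradiction stays in the text.

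**The consequences are limited.** This stands for the 50% responder endpoint: both analyses will be reported, the p-values are unadjusted, and the primary endpoint is not involved. It does not cover the endpoints for which no sensitivity analysis is listed. The HIT-6 clash is conditional, because 9.5.4 points to 9.5.2, which states no rule.

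**The illustration favours divergence.** The 30% vs 43% cases sit near p=0.05, and proration of months with at least 14 diary days will hold missingness down. With 3% missing in both arms the p-values are 0.043 and 0.045. With 4%/6% at 30% vs 45% they are 0.022 and 0.032. This is fair: the figures show possible size, not expected size. Even so, 4%/6% at 30% vs 43% gives 0.045 and 0.063.

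**SAP 8.3.3 is also loose.** It describes non-responder imputation without naming its role in that sentence. SAP 8.3 has already placed the method among the sensitivity analyses.

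**Redaction, and another repair.** The code appendix and parts of Section 9 are redacted, so a difference in proportions may be planned there, and the crude difference can be read from the tabulated percentages. The mismatch could also be closed by changing the summary measure in SAP 2.1 to the odds ratio. Both points stand. They do not change what the visible text plans.

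**Conclusion.** The concern holds on both parts and should be fixed. The SAP gives incompatible missing-data rules for the primary analysis of the 50% responder endpoint, and the visible text plans no stratified difference in proportions with a confidence interval, although SAP 2.1 names that difference as the target. The text conflict needs no assumption. Its numerical size does: in the assumed cases with 6 to 10 points of imbalance in missingness, the estimated difference moves by about 1 to 5 points and a nominal result can cross 0.05 in either direction, while 6% missing in both arms moves it by under 1 point. The second part is limited to unredacted text. The primary endpoint analysis and the 0.10 family-wise error rate are not affected.

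**What to change.** Before unblinding:

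1. In the week-12 paragraph of SAP 9.5, replace the non-response imputation clause with a statement that the stratified CMH test uses observed data. Write the same rule into the primary column of Table 9-1 and into 9.5.2. Keep CMH with non-responder imputation as the named sensitivity analysis. This follows the sponsor's own rule in 8.3, the 9.5 methods table and Section 10. Making imputation primary would be a different choice, needing declared changes in all those places and in Table 9-1; it is not requested here.
2. In SAP 9.1, 9.5 and Table 9-1, add the Mantel-Haenszel stratum-weighted difference in proportions with a 95% confidence interval, using the CMH strata (region and CM/EM), as the estimate matching SAP 2.1. Keep the odds ratio as supplementary.

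The cost is one clause, the same wording in two other places, and one extra output line per dichotomous endpoint. The drawback is that two effect measures appear for one endpoint, so the SAP must say that the difference is the estimand and the odds ratio is supplementary.

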**EM is defined as:**

- $< 15$  headache days of which at least 4 or more headache days meet criteria as migraine days during the baseline period based on the eDiary calculations

108 Demonstrated at least 80% compliance with the eDiary (for example, completing eDiary items for at least 23 out of 28 days during the baseline period)

### 6.4 Exclusion Criteria Part 2

Subjects are excluded from the study if any of the following criteria apply:

234. Used a prohibited medication, device or procedure during the baseline period (Refer to [Section 7.1.7](#) for the list of these excluded treatments and the timeframes)
235. Received botulinum toxin in the head and/or neck region during the baseline period
236. Taken opioid- or butalbital-containing analgesics or other narcotics (including tramadol, Fiorinal, Fioricet) on  $\geq 4$  days per month for any indication in any month during the baseline period
237. Subject has a history or evidence of suicidal ideation (severity of 4 or 5) or any suicidal behavior based on an assessment with the C-SSRS at baseline

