- Change from baseline in monthly mean overall impact on everyday activities as measured by the MPFID stand-alone item
- Change from baseline in monthly days with impact on everyday activities as measured by the MPFID domain
- Change from baseline in monthly days with physical impairment as measured by the MPFID domain
- Change from baseline in the Cranial Autonomic Parasympathetic Symptom (CAPS) scale total score
- Change from baseline in monthly migraine-related disability and productivity as measured by MMIDAS
- Change from baseline in daily activity impact of headache as measured by HIT-6
- Change from baseline in the first 4 weeks in monthly migraine days

Change from Baseline in Mean Monthly Efficacy Measurement over Multiple Months

- The Change from Baseline in Mean Monthly Efficacy Measurement is the Arithmetic mean of monthly values for the months considered - baseline monthly value

Percent Change from Baseline

The change from baseline divided by baseline and multiplied by 100:

$$(\text{Post-baseline} - \text{Baseline}) * 100 / \text{Baseline}$$

If the baseline value is 0 and the post-baseline value is also 0, then the percent change from baseline is set to 0. If the baseline value is 0 and the post-baseline value is non-zero, then the percent change from baseline is set to be missing

Percent change from baseline in (mean) monthly migraine days which is used to determine 50%, 75%, and 100% responder will be calculated as above.

Subject Incidence

The subject incidence for a given event in a given period is defined as the number of subjects with at least one reported occurrence of the event divided by the number of

subjects who entered that period. For subjects with multiple occurrences of the same event, the event will only be counted once per subject.

Medication Overuse at baseline

Medication overuse at baseline will be considered if any of the following criteria are present:

- **≥ 15 days of simple analgesic,**
- **≥ 10 days of triptans,**
- **≥ 10 days of ergotamines,**
- **≥ 10 days of combination therapy intake of any combination of ergotamines, triptans, opiates, combination-analgesic medication (includes the case of more than 1 medication category within one visit).**

Medication Overuse during the DBTP

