Change from baseline in monthly days with impact on everyday activities as measured by the MPFID
Change from baseline in the monthly average overall impact on everyday activities score as measured by the MPFID
Change from baseline in the Cranial Autonomic Parasympathetic Symptom (CAPS) scale total score

^b The same analyses methods will be applied to the endpoints:

Response defined as a 100% reduction from baseline in mean monthly migraine days
Achievement of at least a 5-point reduction from baseline in mean monthly average physical impairment scores as measured by MPFID
Achievement of at least a 5-point reduction from baseline in monthly average impact on everyday activities scores as measured by MPFID

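### In months with 14 to 27 diary days, proration leaves zero migraine days at zero, so 100% response can be misclassified only upward

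*SAP*

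**What the plan says.** SAP Section 8.3 gives the monthly count as "Number of observed migraine days *28/Number of information days in interval". Table 8-1 sets the condition: "interval post baseline ≥ 14 (including retrospective eDiary days), then do proration"; otherwise "Else monthly measurement is set to missing". The denominator is wider than the condition, since an "information day is a diary day or headache day".

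SAP Section 5.6 carries the prorated value into the responder endpoints: "Percent change from baseline in (mean) monthly migraine days which is used to determine 50%, 75%, and 100% responder" comes from the same percent-change formula. Complete response is defined in SAP Section 5.1.1 for the final four weeks of double-blind treatment. In Table 9-1 footnote b it is "Response defined as a 100% reduction from baseline in mean monthly migraine days". If that mean spans several months, every month averaged must be zero, but the proration issue is the same.

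At entry, Protocol Section 6.3 (criterion 108) asks for 80% diary compliance, for example "completing eDiary items for at least 23 out of 28 days". After baseline, the only completeness rule I found is the 14-day minimum. The partly redacted Table 9-1 row to which footnote b appears to belong lists observed-data summaries, a stratified CMH test and no sensitivity analysis.

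**The concern.** Proration is a reasonable correction for a non-zero count: one migraine day in 14 recorded days becomes 2.0. It has no effect on zero, and zero is the only value that defines complete response. A truly migraine-free month always shows zero, however many days are recorded. A month with migraine can also show zero if the migraine days are the unrecorded ones. So among months that pass the 14-day rule but are incomplete, false complete responders arise and false non-responders do not.

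Non-responder imputation (SAP Section 8.3.3) does not touch these months, because they are not missing. SAP Table 5-1 also ends the week-12 interval at the earlier of Day 84 and end of study. A subject who leaves mid-interval after 14 migraine-free diary days can therefore qualify.

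Readers will take 100% reduction to mean migraine-free for the month. The plan allows that label with half the month unobserved.

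**Working it through.** The documents state no 100% response rate and no post-baseline missingness rate, so there is no plan figure to reproduce.

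**Zero stays zero.** 0 × 28/n = 0 for every n from 14 to 28. Eligibility requires at least 4 baseline migraine days (at least 8 for chronic migraine), so the baseline is never zero. For baselines of 4, 8 or 18, (0 − baseline) × 100/baseline = −100%, which is complete response.

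**Chance of a false complete response.** Take m true migraine days in 28 and n recorded days, and assume the recorded days are a random subset. Then P(none observed) = C(28−m, n)/C(28, n).

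| True days m | n = 14 | n = 20 | n = 23 | n = 28 |
|---|---|---|---|---|
| 1 | 14/28 = 50% | 28.6% | 5/28 = 17.9% | 0% |
| 2 | (14×13)/(28×27) = 24.1% | 7.4% | (5×4)/(28×27) = 2.6% | 0% |
| 3 | (14×13×12)/(28×27×26) = 11.1% | 1.7% | (5×4×3)/(28×27×26) = 0.3% | 0% |

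With 8 true days and n = 14 it is 0.1%. Only subjects close to migraine-free are affected.

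**Effect on the overall rate.** The following are assumptions, not figures from the documents. True monthly counts are negative binomial (cut off at 28), recorded days are random, and completeness is unrelated to the true count. The last two columns add 10% of subjects with fewer than 14 diary days to the 10% with 20-day months. All rates are percentages.

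| Mean / size | True rate | 10% at 20 days | 10% at 14 days | Added <14: observed data | Added <14: non-responder imputation |
|---|---|---|---|---|---|
| 5 / 2 | 8.17 | 8.62 | 9.26 | 8.67 | 7.80 |
| 8 / 2 | 4.04 | 4.30 | 4.71 | 4.33 | 3.90 |
| 10 / 3 | 1.25 | 1.38 | 1.62 | 1.39 | 1.25 |

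For the middle row, the apparent rate within 20-day months is 6.64%:
- 10% partial only: 0.9 × 4.04 + 0.1 × 6.64 = 4.30.
- Adding 10% below 14 days, non-responder imputation: 0.8 × 4.04 + 0.1 × 6.64 = 3.90.
- The same, observed data: 3.90/0.9 = 4.33.

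The observed-data rate can also fall. If 100 subjects include 5 true complete responders, and 1 of those 5 is among 10 excluded subjects, the rate is 4/90 = 4.4% against a true 5%.

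**Comparing remedies** (middle row, 10% at 20 days, none below 14):
- Current rule: 4.30 − 4.04 = +0.26 points.
- 23-day rule for zero-count months only, set to non-response: 0.9 × 4.04 = 3.64, or −0.40 points.
- The same, set to missing: 3.64/(1 − 0.1 × 0.0664) = 3.66, or −0.38 points.
- 23-day rule for all months, observed data: (0.9 × 4.04)/0.9 = 4.04, no bias.

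**The case against.** A reader might infer that incomplete diaries can only raise the complete-response rate, that it is overstated in every arm, and that falling diary use will look like efficacy. The documents do not support this. Below 14 diary days the month is set to missing. SAP Section 8.3.3 and the text before Table 9-1 then make it a non-response, and an observed-data analysis drops it. The first lowers the rate, and the second can move it either way. The net direction depends on the mix of partial and missing months.

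Other points for the plan also stand:
- The 50%, 24% and 11% figures apply at the 14-day floor to subjects with one to three true migraine days. The trial admits only subjects with at least 80% baseline compliance. Retrospective entries count as diary days, and a headache logged on an otherwise incomplete day is still an information day, so a recorded migraine blocks complete response.
- With an active arm of about 100 (335 × 0.3), +0.26 points is about a quarter of a subject.
- Complete response is neither primary nor among the secondary endpoints in SAP Section 2.1. The trial is double-blind, and nothing in the documents suggests that diary compliance will differ by arm.
- The 23-day figure is an eligibility example, not a validated analysis cut-off. At exactly 23 days it still leaves an 18% chance of a false complete response for one true migraine day.

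These points limit the size and importance of the issue. They do not remove the one-way error among months with 14 to 27 diary days, which the planned analyses would not reveal.

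**Conclusion.** The point holds for months that pass the 14-day rule but are incomplete: there, misclassification of 100% response runs upward only. It does not extend to the overall rate, whose direction is open. Under the assumptions above, 10% of subjects with 20-day months add 0.13 to 0.45 points to true rates of 1.25% to 8.17%. At the 14-day floor they add 0.37 to 1.09 points.

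Bias in the treatment comparison generally needs diary completeness, or the distribution of true counts, to differ by arm. The primary endpoint is not affected in this one-way manner. This is a minor, inexpensive improvement.

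One related inconsistency matters because it decides what happens below 14 days. The SAP Section 9.5 text before Table 9-1 applies the CMH test to dichotomous endpoints after non-responder imputation. The methods table in the same section (for the 50% response) and SAP Section 10 (for categorical secondary endpoints) use observed data. Which rule governs 100% response is not clear.

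**What to change.** For 100% response, add an observed-data analysis in which a month is evaluable only with at least 23 of 28 diary days, the 80% level of criterion 108. Apply it to every month regardless of the observed count. Restricting it to zero-count months would exclude subjects according to their outcome and, in the example above, bias the rate downward by more than the amount it removes. Report this analysis beside the 14-day rule, and tabulate diary days among 100% responders by arm. State which missing-data rule applies to the CMH test for this endpoint, and align SAP Sections 8.3.3, 9.5 and 10.

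The cost is about a sentence in the SAP for the added analysis, a short clarification of the CMH rule, slightly fewer evaluable months and a little more analysis work. No new data are needed. The remedy removes nearly all of the bias only if unrecorded days are random and completeness is unrelated to migraine frequency, which is why both versions should be shown.
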